2.2 Preclinical Data

t-PBM Effects on Animal Models of Depression: Multiple pre-clinical studies support the efficacy of t-PBM, in single or repeated administration, on animal models of depression such as the forced swim test^{24,27,90,98}, tail suspension test^{27,90}, mild chronic stress^{26,28}, or the reserpine-induced depression²⁴. In several of these studies the antidepressant effects were associated with biological effects related to mitochondrial stimulation, such as increased ATP biosynthesis and mitochondrial complex IV expression and activity in the prefrontal cortex (PFC)²⁷ and increased hippocampal neurogenesis⁹⁸.

t-PBM NIR with laser devices have good penetration. NIR (808 nm) was detected 4 cm below the skin in unfixed cadaver brains (n = 8) with a 5-W laser; the penetration at 808 nm (NIR) wavelength was superior to the 940 (NIR) and 660 nm (red) light¹⁴. Also, a 15-W laser produced a 2.9% penetration of NIR (810 nm) at 3 cm from skin surface of recently slaughtered sheep heads¹². Moreover, pulsed wave (PW) delivery might allow higher penetration than continuous wave (CW), by increasing peak irradiance and by lowering skin warming, which would limit light exposure⁵². The penetration for LED devices has been more variable^{12,13}, which supports our decision to use lasers for this application.

[figure not shown]
2.3 Clinical Data to Date

Evidence of Efficacy in Depression: All clinical studies using t-PBM for MDD reported in the literature aimed to modulate the forebrain, consistently with the dysfunction of the PFC associated with MDD⁹⁹. [name] conducted a proof of concept, prospective trial on the safety and efficacy of adjunct t-PBM NIR (810nm) delivered to PFC, twice a week for 3 weeks in subjects with MDD, demonstrating the feasibility and safety of t-PBM in this population. In this investigation, mean HAM-D17 scores decreased from 19.8 ± 4.4 (SD) to

13 ± 5.35 (SD) after treatment ($p=0.004$).

Patients tolerated the treatment well without any serious adverse events. Our recently published RCT showed t-PBM was more efficacious than sham in 21 MDD subjects receiving bilateral t-PBM at 823 nm or sham directed on dorsolateral PFC (dIPFC) (EEG sites F3 and F4) twice-a-week for 8 weeks³⁵. Completer analyses showed a significantly greater decrease of depression scores per the HAM-17 in the NIR-mode compared to sham [NIR (n=6) -15.7 ± 4.41 vs. sham (n=7) -6.1 ± 7.86 ; $p=.031$]. Further, t-PBM was well tolerated, with no serious adverse events. The effect size was large (Cohen's $d=1.5$) and reached significance with an $n=13$

Figure 2: BOLD fMRI Imaging Pre and Post tPBM

(Figure 1). Another randomized, controlled study suggested that t-PBM paired with a cognitive therapy may be effective in depression³⁴. All these studies measured acute, short term effects; only a case report describes persistence of effects over 9 months of repeated administration in a subject with MDD and anxiety³².

Impact: *These data support the eventual clinical utility of t-PBM and highlight the importance of determining optimal parameters, as proposed in this application.*

Preliminary data on t-PBM effect on Cerebral Blood Flow (measured with fMRI-BOLD): We have collected data from n=20 subjects undergoing tPBM during resting state fMRI¹⁰³. To disambiguate the effects of CBF from those of blood oxygenation, we employed a multi-echo MR sequence¹⁰⁴. Subjects' brain activity in the form of the BOLD signal was acquired continuously for 30 minutes, with tPBM applied for 10 minutes beginning at minute 11. Stimulation was delivered with a laser (808 nm), with an intensity of 318 mW/cm² and a spot size of 1 cm² to the right forehead (standard EEG electrode location "Fp2"). Whole-brain voxel-wise statistical Chow tests¹⁰⁵ were conducted separately at each echo of the group-averaged BOLD in order to detect significant changes during and after t-PBM, relative to the pre-stimulation baseline period.

During t-PBM, we found a significant modulation of early-echo (13 ms) BOLD in a cluster of 214 voxels in the right medial frontal gyrus (MFG), 24 mm from the site of light incidence (Figure 2). A cluster of 154 voxels in the right MFG, 22.4 mm from incidence, was also found at echo 2 (34 ms). Four smaller clusters were detected at echo 3 (56 ms), including one in the right superior frontal gyrus (SFG), 22.5 mm from incidence. Interestingly, we found that t-PBM produced an effect on the early-echo BOLD that outlasted the stimulation. A cluster of 218 significant voxels centered in the MFG was found at a distance of 28.7 mm from incidence. The presence of significant BOLD effects at all echos, including the early-echo which is insensitive to blood oxygenation, suggests that CBF was increased during and after t-PBM.

Impact: *Thus, we are in a position to employ quantitative changes in fMRI-BOLD as a biomarker for target engagement during t-PBM.*

Evidence of t-PBM Safety and Tolerability: The safety of one session of t-PBM was evaluated in three large RCTs with a pooled sample of 1,410 subjects with stroke^{21,22,100}. No significant difference in the rate of adverse effects were observed between the group receiving laser NIR (808 nm; 5W) or sham. No serious adverse events were found in our review of the literature³³. Two open studies using 1 and 6 sessions of t-PBM reported no treatment-emergent side-effects^{29,30}. A clinical trial with 16 sessions reported an increased number of mild side-effects in the active treatment group, the most frequent being insomnia, "seeing vivid colors", "an ashtray-like taste", and irritable mood³⁵. Other potential risks relate to inappropriate administration and will be mitigated by the safety procedures such as the use of protective eye wear. The risk of thermal injury from PBM delivered with the parameters used in the studies we reviewed is considered minimal and limited to the skin. In ten individuals treated for TBI with 10-15W lasers – a much higher power than what is used in t-PBM – the skin temperature increased to no more than 30°C with rapid cooling after removal of the NIR light. Clinically, patients reported slight skin warming, but no discomfort¹⁰¹. Inherent to the use of any laser device is the potential risk of retinal lesions resulting from improper use of the laser and from the shedding of the light beams straight through lens and from their convergence on the macula; this is mitigated with appropriate safety eyewear and procedures.

2.4 Dose Rationale

As depicted in Table 1, all t-PBM sessions will incorporate: **1.** laser light with **2.** a wavelength of 808nm, corresponding to the absorption peak of the primary photoreceptor cytochrome-C oxidase **3.** and target bilaterally the dlPFC (standard EEG electrode sites F4, F3). The total area of exposure, as a result, will also remain constant at 24cm² (12 cm² bilaterally).

The irradiance will vary across three experimental doses (50, 300, and \geq 700 mW/cm²) therefore also impacting the exposure time, fluence, and total energy. The low and medium doses will both be administered in continuous wave mode; the high dose will be administered in pulsed wave mode (\geq 700mW/cm²). .

Rationale for Constant t-PBM parameters: We will use a laser source of NIR since, in contrast to LED devices, lasers on optic fibers are MRI-compatible and can more easily produce high irradiation (e.g. 700 mW/cm²). The 808 nm NIR wavelength is at the absorption peak of the primary photoacceptor cytochrome-C oxidase⁵⁵, has optimal penetration through the skull^{12,14}, and proven effects on CBF (BOLD signal)¹⁰³ and on mood^{30,35}. We chose to broadly irradiate and engage the PFC, since: 1) the aforementioned areas are all involved in emotion-regulation processes⁹⁹; 2) abnormalities in CBF, which are well-documented in MDD patients, involve broadly PFC^{38,39,41}.

Rationale for Irradiance Doses: t-PBM at irradiance doses of 50 mW/cm² had significant effects on mood^{29,30} and cognition¹⁰⁸; t-PBM at 300 mW/cm² have been associated with changes in CBF¹⁰³ and on cognition^{107,109}, while irradiance doses of 700 mW/cm² have been effective in depression³⁰ and in large studies in stroke^{21,22,100}. All three doses have been safely used in adults. Therefore, the three irradiance doses proposed (50, 300, and \geq 700 mW/cm²) cover the full spectrum of doses in the literature, enabling us to determine the optimal dose for target engagement

Rationale for Wave Form Selection: We will use continuous wave (CW) NIR for the low and medium doses, which is supported by a preponderance of current data..

We will use a pulse wave for the high dose because pulsing can prevent skin warming and discomfort thus facilitating enrollment and retention and safeguarding the integrity of the single blind. Safety data from three previously referenced stroke RCTs including 1,410 participants^{21, 22, 100} offer ample evidence that a 700 mW/cm² continuous wave dose is safe. However, testing during the development of our study-specific device suggests that some participants may experience it as “hot” and/or unpleasant and be able to distinguish it from the sham and lower doses. Offering the pulsed high dose instead allows us to expose participants to a similar peak irradiance while lowering the average irradiance, thus reducing the likelihood of inducing skin warming or discomfort.

Table 1. t-PBM Parameters Across 4 Sessions

Parameters	Dose				
	High	Middle	Low	Sham	
Peak Irradiance (mW/cm ²)	833	300	50	0	
Average Irradiance (mW/cm ²)	275	300	50	0	
Time Irradiation (s)	600	333	1200	0	
Average Fluence (J/cm ²)	165	100	60	0	
Total energy (kJ/ cm ²)	2.0	2.4	1.4	0	
Wave Mode	Pulsed	Continuous	Continuous	N/A	
NIR source	Laser	Laser	Laser	N/A	
Wavelength	808nm	808nm	808nm	N/A	
Area of exposure	24cm ²	24cm ²	24cm ²	N/A	
Anatomical targets	F4, F3	F4, F3	F4, F3	F4, F3	

2.5 Rationale

Why test t-PBM parameters with BOLD fMRI

A novel or innovative therapy would not be clinically justified unless it adds significant value in terms of risk/benefit. The limitations of current treatments in MDD are well-documented [Section 2.1.1]. Preliminary data suggests t-PBM targeting the PFC could be a novel treatment strategy in MDD [Section 2.2.1 and

2.2.2]. However, the t-PBM parameters that would maximize its neural impact and therefore its antidepressant potential are not known. Therefore, this study will apply a novel measurement of changes in BOLD fMRI signal as a marker of changes in CBF in the search for optimal t-PBM parameters, with the **long-term goal of transforming clinical practice for patients with MDD**. Proof of engagement of CBF on PFC would support future clinical testing of this low-cost, time-efficient, accessible and user-friendly intervention in MDD subjects.

We considered alternative measures of CBF, including near-infrared spectroscopy (which is associated with much poorer spatial resolution and can only evaluate CBF changes in the superficial cortex in adults), or PET/SPECT (where changes in CBF over a short period of time would be difficult to quantify, and repeated weekly administrations would be limited by the total dose of radiation). We believe the method we propose offers the best balance of accuracy, spatial resolution and repeatability. In our preliminary data, we found a strong effect at echo 1 (Cohen's $d = 1.54$, when comparing the echo 1 BOLD immediately before light onset with the BOLD 200 seconds after onset, (Fig.3).

[figure not shown]

Fig. 3: Time series of BOLD changes after t-PBM was applied to the right forehead 10 min. into a 30-min. BOLD scan¹⁰³. The duration of stimulation was 10 min. (grey area). The colored time series indicate the subject-averaged BOLD (shown here in a ROI corresponding to the right medial frontal gyrus, MFG) at echos 1 (blue, 13 ms), 2 (red, 34 ms), and 3 (orange, 55 ms). A rapid increase in the BOLD was observed shortly after stimulation onset, while a second peak emerged later in the 10 min. stimulation window.

The project is innovative because (1) it tests t-PBM with near-infrared light, an innovative technology with a well-established safety profile, and (2) it uses changes in CBF, as measured with changes in BOLD fMRI signal, as a state-of-the-art target engagement biomarker.

2.6 Potential Risks & Benefits

2.6.1 Known Potential Risks

General: By agreeing to participate in this study, subjects temporarily forgo the opportunity to receive regular psychiatric care in the community. For patients with major depressive disorder resistant to medications, alternative options would include ECT, VNS, rTMS, and additional augmentation strategies (psychotherapies, atypical antipsychotics, lithium, T3). The alternatives to this research are clearly explained to all patients, and treatment strategies that are generally used for these patients are discussed. Subjects are informed that t-PBM is not FDA approved for any psychiatric disorder and would therefore not be recommended for use after the study.

Screening and Evaluation: The risks and discomforts of the screening evaluations include discomfort or distress responding to potentially sensitive questions regarding mental illness and drug use. Research interviews are interrupted if individuals become distressed or object to answering questions.

Delay in Initiation of New, or Changes in Ongoing, Antidepressant Treatment: While this study is not testing t-PBM as a treatment for depression, an antidepressant effect of t-PBM is possible. Any delay in receiving t-PBM (while screening procedures are completed) might be considered as a delay in treatment from a patient perspective. We will emphasize that the study is not geared to test a treatment but instead the impact on cerebral blood flow of t-PBM.

Further, study participation requires stable antidepressant treatment. It is therefore possible that the participant's condition could worsen and lead to increased disturbances in mood, anxiety, sleep, appetite, energy and cognition. This could result in work loss, loss of social function, and possibly increased risk of suicide. However, the risk should be minimized as there are several safety precautions in place and participants will have frequent contact with study clinicians.

Risks of Clinical Decompensation: If a patient has worsened to such a degree that further participation would put him or her at risk, then he or she will be discontinued from the study. In such cases, the patient is immediately transferred to standard clinical treatment and exited from the research. At any point during the study, patients are told to immediately inform their study psychiatrist if they develop worsening of depression or anxiety, symptoms of mania or psychosis, or active suicidal plans.

Risks of t-PBM: The study laser device emits light with a longer wavelength than the human eye can see. The staff will be provided training on basic safety procedures relative to the use of the device. The staff administering the t-PBM will be careful not to operate the laser unless it is in direct contact with the subject's skin. Protective eyewear is required since the device is a laser. Failure of laser device, resulting in the cessation of investigative therapy can cause no adverse event to our knowledge. Delivery of the infrared laser energy to an inappropriate site, such as directly over the open eye, would pose risk to the subject, such as blindness. Based on previous observations with similar laser devices, application of the laser may result in mild thermal sensation of warmth during use. The temperature of the skin is however kept well below the level for thermal damage. Based on human clinical trial experience to date and on sale of t-PBM devices for their intended use (e.g. Omnilux New-U), each adverse event listed below has been reported by less than 0.1% of all subjects and users: erythema, pain, discomfort, warmth, headache or other reactions at the application site. In our research experience, t-PBM devices could produce insomnia, irritability and fleeting illusions. The modality of administration for the t-PBM with the study laser device is analogous to the protocols used in our feasibility studies. The dose of light delivered by the study device is analogous to our feasibility studies and to published studies on t-PBM. No serious adverse events occurred during our feasibility trials.

The MGH and NKI sites have extensive experience in transcranial photobiomodulation. The MGH Wellman Center of Photomedicine conducted the first open study on t-PBM in subject with clinically-significant mood symptoms. At the MGH DCRP, [name] has conducted two studies on t-PBM in subjects with clinically-significant mood symptoms, also in collaboration with [name] (NKI/ NYU).

Risks of MR: The risks associated with the MRI procedure are minimal. Subjects who have non-MRI compatible metal implants, cardiac pacemakers, and potential pregnancy will be excluded. Some patients experience claustrophobia (fear of being in a closed space) while inside the machine. In these cases, the examination will be terminated immediately, and the participant will be rapidly removed from the scanner.

2.6.2 Known Potential Benefits

All study participants receive without cost an extensive psychiatric and medical evaluation. No other direct benefits result from study participation. The possible benefits to the patient (remission or improvement of mood and anxiety symptoms) and to others (development of new treatments with sound target engagement of the brain) are reasonable in relation to the risks of this study. The intervention itself with tPBM may potentially provide relief of mood and anxiety symptoms, at a level equal to antidepressant medication.

3 Objectives and Purpose

3.1 Primary Objective

Our primary objective is to identify the t-PBM irradiance dose (50, 300, or ≥ 700 mW/cm 2) with the largest impact on PFC CBF in MDD.

3.2 Secondary Objective

Our secondary objective is to compare the safety and tolerability of three t-PBM irradiance doses.

3.3 Exploratory Objectives

Our exploratory objectives are to compare the effects of three t-PBM doses on depression symptom severity, anxiety symptom severity, and quality of life.

3.4 Description of Study Design

We will compare the effect of three t-PBM doses (high, middle, and low irradiance) to sham t-PBM on PFC CBF as assessed with fMRI (BOLD) in this multi-center, phase I, single-blind, dose-ranging, crossover study of 30 subjects with MDD. All eligible participants will undergo four sessions of t-PBM during fMRI so that they experience irradiances of 50, 300 and ≥ 700 mW/cm 2 as well as sham. The order of dose administration will be randomized and t-PBM will be administered with the LightForce® EXPi Deep Tissue Laser Therapy™ System, Transcranial PhotoBioModulation-1000 (tPBM-2.0).

3.5 Study Endpoints

3.5.1 Primary Study Endpoints

The primary endpoint will be t-PBM effects on BOLD signal.

The specificity of t-PBM effects on BOLD signal increases will be assessed by testing three irradiance doses covering a wide range (50, 300 and ≥ 700 mW/cm 2) versus sham. If a reliable effect on BOLD (compared to sham, the BOLD increase at the optimal dose will have an effect size of Cohen's $d \geq 0.5$) is seen with PBM, the study validate BOLD fMRI as a robust biomarker of target engagement for t-PBM and act as a "go" signal. In contrast, if none of the t-PBM doses yield reliable BOLD increases, this will fail the putative mechanism (*no go*).

Rationale for the effect size (E.S.) threshold: We have previously observed large effect size changes in BOLD (Cohen's $d=0.6$) after a single administration of t-PBM (at 318 mW/cm 2)¹⁰³. In our clinical pilot study, significant, large effect size improvements in depressive symptoms were reported in MDD after 8 weeks (Cohen's $d=1.5$, $n=21$)³⁵. Given these preliminary results, we will use as threshold for the Go/No-Go decision an effect of t-PBM on BOLD at one dose (but not all doses, vs. sham) of magnitude Cohen's $d > 0.5$ (at least medium size).

3.5.2 Secondary Study Endpoints

The secondary endpoints will be t-PBM effects on brain temperature, suicidal ideation/behavior, and the frequency and severity of adverse events and side effects occurring at the time of each t-PBM session and between each t-PBM session and the subsequent study visit. Brain temperature will be assessed with MR; suicidal ideation/behavior with the C-SSRS. Adverse events will be tracked with the adverse events log; side effects, with the SAFTEE and TSRQ.

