4.4 Duration of Study Participation

Study participation should last between six and twelve weeks. Participants are required to attend one remote screen visit and five clinic visits (second screening visit and four scanning/t-PBM sessions) and answer questions during a single follow-up phone call. If scheduled for consecutive weeks, participants will complete the study in six weeks. However, for logistical regions the time between screening completion and the first scanning/t-PBM session can be as long as four weeks; in addition, as long as two weeks may pass between each scanning/t-PMB session.

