6.2.3 Experimental Phase

Duration: 4 visits over 4-8 weeks

Timing: No more than 2 weeks between each visit.

While the provision of study treatment requires clinic attendance, we may conduct other components of the experimental visits remotely.

At each of the four visits, study staff will:

- *Record vital signs;
- Administer
MADRS,
CGI-I (except Visit 1 as this will be considered a baseline rating),
CGI-S,
C-SSRS, and
- MRI Safety Checklist; Record concomitant medications/therapies;
- *Administer the t-PBM session during MR Scanning;
- Record adverse events as reported by participant or observed by investigator.

In addition, participants will complete:

- PANAS,
- PBQ
- PCQ
- SDQ,
- ASQ,
- SAFTEE

- Neuro-QoL
- Q-LES-Q-SF, and
- TSRQ

MGH Site Neuronavigation: The BrainSight Neuronavigation System will be used at the MGH site to track the initial placement of the laser device on the subject's forehead and will be utilized to ensure accurate replication of positioning at each experimental visit. This is a recording device that does not involve any added risk or stimulation. Traditionally, this device is used to record precise location of EEG electrodes and transcranial magnetic stimulation (TMS) coils. In our case, we will be using it to record the position of the outlet of the laser before every PBM session. The BrainSight Neuronavigation System is FDA approved and is used as indicated. This device bounces light off of trackers that are placed on the forehead. Study staff lightly place a wand at various spots on the head. The system correlates the position of the wand with that of the trackers to precisely record the location of the head in relation to the photobiomodulation stimulation device. This is useful for later analysis, in which we will co-register the recorded laser position to the subject's MRI.

- For the NKI/NYU scans, lipid capsules are affixed to the device for demarcation of device location in the scans.

MR: Scanning will begin with acquisition of structural images and (for most subjects) a baseline MR thermometry scan. Subsequently we will collect approximately 60 minutes of functional data collection including ~20 minutes before t-PBM, ~20 minutes coinciding with t-PBM, and ~20 minutes following t-PBM, as well as (for most subjects) a post-t-PBM MR thermometry scan. (For technical and logistical reasons, we may opt to skip the thermometry scan for some subjects.)

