6.2.4 Follow-up Phase

Duration: 1 phone call

Timing: Within one week of fourth t-PBM/scan session

Over the telephone study staff will administer the

- CGI-I
- CGI-S
- MADRS, and
- C-SSRS, and
- record concomitant medications/therapies and any adverse events.

Participants will also complete the following self-report scales remotely using Acquire:

- PANAS
- PCQ
- SDQ,
- ASQ,
- SAFTEE,
- Neuro-QoL

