7.3 Time Period and Frequency for Event Assessment and Follow-Up

The occurrence of an AE or SAE may come to the attention of study personnel during study visits and interviews of a study participant presenting for medical care, or upon review by a study monitor. All AEs including local and systemic reactions not meeting the criteria for SAEs will be captured on the appropriate RF. Information to be collected includes event description, time of onset, clinician's assessment of severity, relationship to study product (assessed only by those with the training and authority to make a diagnosis), and time of resolution/stabilization of the event. All AEs occurring while on

study must be documented appropriately regardless of relationship. All AEs will be followed to adequate resolution.

Any medical condition that is present at the time that the participant is screened will be considered as baseline and not reported as an AE. However, if the study participant's condition deteriorates at any time during the study, it will be recorded as an AE. UPs will be recorded in the data collection system throughout the study.

Changes in the severity of an AE will be documented to allow an assessment of the duration of the event at each level of severity to be performed. AEs characterized as intermittent require documentation of onset and duration of each episode.

The PI will record all reportable events with start dates occurring any time after informed consent is obtained until 7 (for non-serious AEs) or 30 days (for SAEs) after the last day of study participation. At each study visit, the investigator will inquire about the occurrence of AE/SAEs since the last visit. Events will be followed for outcome information until resolution or stabilization.

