The DSMB will review adverse events (AEs) and serious adverse events (SAEs) as recorded in the adverse events logs as well as, other data that may reflect differences in safety between treatment groups. This includes treatment retention rates, reasons for drop-out, and laboratory values reflecting potential toxicity.

Serious Adverse Events

Expedited review will occur for all SAEs. For purposes of this study, all SAEs will be reported to the DSMB, regardless of any judgment of their relatedness to the study intervention. All relevant information will be reported to the DSMB for each SAE including information about the event and its outcome, dosing history of the study intervention, concomitant medications, the subject's medical history and current conditions, and all relevant laboratory data. Notification by e-mail and fax transmittal of all related study forms shall be made to the DSMB within 7 days of the occurrence of any SAE. Information will be reviewed and a determination made of whether there was any possible relevance to the study intervention.

Non-Serious Adverse Events

At periodic intervals (biannually during the course of the study and then again at its completion), the DSMB will be provided with unblinded summaries of the numbers and rates of adverse events by treatment group. These reports will include types of events, severity, and treatment phase. Data on individual non-serious adverse events is not expected to be needed for this review.

Other Safety-Related Reports

Biannually, the DSMB will also receive unblinded summary reports of treatment retention reasons for drop-out, and laboratory values reflecting potential toxicity by treatment arm.

Monitoring of Data Quality by the DSMB

During the course of the study, the DSMB will receive reports on data quality and completeness. At a minimum, these will include an overview of the progress of patient intake and retention; summary reports describing patient adherence with visits, evaluations, and dosing as described in the protocol; and a summary of the completeness and quality of key data elements needed to characterize patients, their dosing, and their primary and secondary outcomes. These reports will be used by the DSMB to evaluate the capacity of the data capture and processing to support scientifically valid analyses.

Annual DSMB Report to Sponsor

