9.3.3 Analysis of the Secondary Endpoint(s)

For each subject at each t-PBM dose (including sham) we will compute changes in brain temperature using data recorded just before and after the t-PBM administration with MR thermometry scans.(Note that for technical and logistical reasons, some subjects may not undergo MR thermometry.) We will quantify the frequency and severity of suicidal ideation experienced as well as the presence or absence of suicidal behaviors after each t-PBM session using the C-SSRS. Finally, we will use the SAFTEE, TSRQ, and adverse events logs to determine the frequency and severity of side effects and adverse events. We will model these measures as a function of dose (considered a categorical variable with 4 levels) using mixed effects models¹¹⁷, including random subject intercepts to account for the potentially correlated measures on the same subject. Since the doses will be presented to subjects in a random order, the initial models will also include order of the dose (a continuous variable) and all interactions between the dose and the order. If there is evidence for an interaction effect between dose and order, this effect will be investigated to understand how the dose effect varies as a function of week of treatment, and in such case effect size of the t-PBM doses will be estimated using only the data when the dose was given in the first week. Whenever we find there is no interaction between dose and order, the order variable and the interactions will be omitted. The resulting models will be used to estimate the mean of each measure at each dose and the differences between each active t-PBM dose and sham.

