14.3 Participant Reimbursements or Payments

Patients are compensated for expenses of parking and travel associated with study participation, at a rate which is reasonable, however unlikely to induce coercion for research participation. We will compensate each subject \$50 for screening and \$75 for each MRI they complete (up to 4 MRIs per subject for a total of \$300) for time, effort and inconvenience. Subjects will also be reimbursed for transportation costs at each visit (maximum \$50 per visit). Finally, each subject will receive \$50 for completion of the follow-up visit, again as compensation for time, effort and inconvenience.

15 Study Administration

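### Adverse events are credited to a dose over unequal windows (up to 14 days after sessions 1-3, at most 7 after session 4), and the model makes no allowance for this

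*Combined protocol and SAP*

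**What the plan says.** - **Endpoint (3.5.2).** The frequency and severity of adverse events and side effects are secondary endpoints. Those credited to a dose are the ones "occurring at the time of each t-PBM session and between each t-PBM session and the subsequent study visit".
- **Elicitation (7.3).** "At each study visit, the investigator will inquire about the occurrence of AE/SAEs since the last visit". The window behind each count is therefore the gap between contacts.
- **Gap after sessions 1-3.** Section 6.2.3 allows "No more than 2 weeks between each visit", and 4.4 says "as long as two weeks may pass between each scanning/t-PMB session". Neither gives a minimum.
- **Gap after session 4 (6.2.4).** There is one phone call, "Within one week of fourth t-PBM/scan session". Section 14.3 pays participants "for completion of the follow-up visit", so the call counts as a visit. After withdrawal, 6.2.5 substitutes the same assessments without stating when.
- **Model (9.3.3).** "We will model these measures as a function of dose (considered a categorical variable with 4 levels") with random subject intercepts. Order enters as a continuous variable with its dose interactions. If there is evidence of interaction, effects are estimated from first-week data only. If not, order is dropped. No exposure time, offset or fixed window is given.
- **DSMB (7.8).** The board receives "unblinded summaries of the numbers and rates of adverse events by treatment group", with no denominator defined.

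**The concern.** Comparing safety and tolerability across doses is the trial's only secondary objective (3.2). A count collected over 14 days is not the same quantity as a count collected over 7 or fewer, yet 9.3.3 treats every session as equal observation. Two things are at stake.

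First, the time observed after each mode can differ by chance within the trial. Fifteen participants per site do not fill blocks of eight orders, up to 20% may drop out, and dropouts are not replaced.

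Second, on a count scale a shorter last window shrinks any true dose difference at session 4. That is a dose-by-order interaction produced by the schedule. The plan's response to such an interaction is to discard everything after the first session, and this is most likely when one mode really is less well tolerated.

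The DSMB has a related problem. Every participant receives all four modes, so rates by treatment group have no evident denominator.

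**Working it through.** The plan gives no figure of its own for this endpoint. The one planning input used is dropout: 30 x (1 - 0.20) = 24, which agrees with 9.4.

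**1. Window lengths.** The maximum is 14 days after sessions 1-3 (4.4, 6.2.3) and 7 days after session 4 (6.2.4), a ratio of 14/7 = 2.0. Both are ceilings. With weekly visits and a call at about day 7, every window is about 7 days.

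**2. Completers at maximum windows.** Eight orders from two 4x4 Latin squares put each dose in each position twice per block. Fifteen per site is two blocks less one order, so across two sites each dose falls in session 4 for k = 6 to 8 people. Person-days = (30 - k) x 14 + k x 7:
- k = 6: 378
- k = 7: 371
- k = 8: 364

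The worst ratio is 378/364 = 1.04.

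**3. Adding dropout and variable gaps.** This is a simulation of 2 sites x 15 participants, with 20% dropout at random after session 1, 2 or 3. Gaps and call days are uniform. These distributions, and an early-termination contact timed like the call, are assumptions because the documents give none. The result is the mean window per session, active divided by sham:

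| Gap (days) | Call (day) | SD of ratio | More than 10% from sham |
|---|---|---|---|
| 7-14 | 1-7 | 0.09 | 27% |
| 13-14 | 6-7 | 0.055 | 7% |
| 7 | 6-7 | 0.009 | 0% |

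The mean ratio is 1.00 to two decimals or very close to it throughout, so no dose is favoured on average.

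**4. Can the order term absorb it?** The least-squares line through windows of 14, 14, 14, 7 has mean 12.25 and slope (-1.5 x 14 - 0.5 x 14 + 0.5 x 14 + 1.5 x 7)/5 = -2.1. Its fitted values are 15.4, 13.3, 11.2 and 9.1. A linear term does not fit a drop confined to session 4, and it is removed when no interaction is found.

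**5. Spurious interaction.** Take illustrative rates of 0.02 and 0.08 events per day. The difference is 0.06 x 14 = 0.84 events over 14 days but 0.06 x 7 = 0.42 over 7. To see how often this triggers the fallback, Poisson counts were simulated under the design in step 3. The dose-by-order term was tested at 5% by least squares, a simplification of the mixed model. Section 9.3.3 sets no threshold, so the 5% level of 9.3.1 is assumed.
- One mode at double the rate (baseline 0.02, 0.05 or 0.10 per day): triggered in 3.2% to 5.8% of trials, against 5.0% to 5.8% with equal windows. There is no inflation.
- One mode at four times the rate: triggered in about 9% (baseline 0.02) to about 25% (baseline 0.10), against about 5-7% with equal windows.

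**6. Cost of the fallback.** By the count in step 2, each dose comes first for 6 to 8 people. The estimate would rest on them alone, as a between-person comparison.

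**The case against.** The strongest reply is that the design already handles this. Position is balanced across doses, so the expected contrast is right and only noise is added. With an assumed 10 events per dose, the standard error of a log rate ratio is sqrt(1/10 + 1/10) = 0.447. Adding the largest simulated SD gives sqrt(0.447² + 0.092²) = 0.457, about 2% wider. The plan also expects weekly sessions (the rationale to exclusion 8 in 4.1, and the 4-week intervention in 9.4), and weekly spacing gives 0% in the table. All of this stands. A reader might infer that the plan biases the comparison towards a particular dose, or that session-4 counts are always halved. The documents support neither.

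A reader might also infer that a dose prompting withdrawal will look safer. If 6 of 30 withdrew just after one mode, its mean window would be (24 x 8.875 + 6 x 4)/30 = 7.9 days against 8.875 (0.75 x 10.5 + 0.25 x 4), a ratio of 0.89. That example is constructed. It puts every dropout after one mode and assumes a 4-day window. The event that prompts withdrawal is itself counted, and the DSMB sees reasons for drop-out.

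A further objection is that days observed may be the wrong denominator. A session lasts 20 minutes, and effects such as warmth or discomfort may cluster soon after it. If they do, counts are already comparable, and a log(days) offset would double the apparent rate in a 7-day window relative to a 14-day one. This also stands, and it is why the offset should not be the primary analysis.

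Finally, 7.3 records non-serious events for 7 days after the last day of participation, so collection may continue beyond the call. But 3.5.2 still ends the per-dose endpoint at the next visit, and nothing links the two rules.

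**Conclusion.** The point holds as a gap in definition with moderate, schedule-dependent consequences. The endpoint window has a 2:1 ratio of maxima between the first three sessions and the last, and nothing in 9.3.3 allows for it. The average dose contrast remains unbiased if withdrawal is unrelated to dose. The effect is close to nil under strict weekly visits. Under the longer gaps that the protocol permits, time observed differs from sham by more than 10% in about 7% to 27% of comparisons, depending on the assumed gaps and call day.

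The more serious consequence is conditional. With a four-fold event rate in one mode, the chance of falling back to first-week data rises from about 5-7% to about 9-25%; with a doubled rate it does not rise. These figures rest on assumed event rates, a constant daily rate and a simplified test. The change is worth making because it costs little and protects the comparison when one mode is poorly tolerated.

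**What to change.** 1. **3.5.2 and 9.3.3.** For the adverse-event log, count onsets within one common post-session window for all four sessions (for example 7 days), using the onset times in 7.3. Credit each event to the most recent session, and report days observed per mode.
2. **6.2.4 and 7.3.** Reconcile the follow-up call, which may fall before day 7, with the 7-day recording after participation, so that the common window is fully observed after session 4. Give the timing of the early-termination contact in 6.2.5.
3. **Sensitivity analysis.** Fit a log-link count model with log(days observed) as offset, and state that it assumes a constant daily rate.
4. **7.8.** Give the DSMB events by mode with sessions and days observed as denominators, in place of undefined group rates.

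The change concerns log counts only. Severity does not suit an offset, and the TSRQ is not scheduled at the follow-up call.

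Cost: mainly wording. Onset times are already collected and session dates are known. The downside is that events after the common window leave the dose comparison and are only listed.
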